# **Duration of study**

The duration of this study will include a 26-week treatment phase and a safety clinic or telephone follow-up visit at week 28.

# Interim analysis

There will be no planned interim analysis of the data.

### **Selection of Patients**

**Number of subjects planned.** The total number of patients with T2D to be included in this pilot study is 150. We anticipate a dropout rate of 10% - 20% through week 24 so that each arm will have 32 subjects at week 32.

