# Methods:

This will be a randomized (1:1), controlled, 26-week cross-over clinical trial in patients with inadequately controlled T2D (HbA1c  $\geq$  7.0% to  $\leq$  12.0%) while treated with oral antidiabetic agents and basal insulin (NPH, glargine or detemir). Participants will be randomized to use the Insulclock device (Group 1) and standard of care using an insulin pen device (Group 2). All patients will use the Insulclock device attached to glargine U100 insulin pens (SoloStar®) during the study period. During the study period. Participants in Group 1 will receive daily information on their smartphone on insulin administration (time and dosing) as well as reminders in the event of missing doses. Participants in Group 2, will use the Insulclock, but will not receive feedback on insulin treatment or alerts.

Randomization will be stratified by:

• HbA1c at Screening (<8.0%, >8.0%)

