### **Power Considerations**

This is a pilot study and we plan to recruit 40 subjects for each study group. Our power calculation is mainly based on the binary primary outcome. We assume no more than 15% attrition rate, and assume no period

effect. In the following table, we give the power for detecting the superiority of Insulclock based on Exact Test for Binomial proportion with alpha=0.05, under different projections for the proportion of subjects showing treatment preference (i.e. adherent under one treatment but not under the other), denoted by Ptp, and projections for the probability of preference to Insulclock given showing treatment preference, denoted by p.

	P tp					
Power		90%	80%	70%	60%	50%
р	0.6	31.2%	28.2%	21.5%	17.8%	13.9%
	0.7	87.9%	83.7%	74.9%	66.5%	55.4%
	0.8	>99%	>99%	>99%	97.6%	93.8%
	0.9	>99%	>99%	>99%	>99%	>99%

Regarding the secondary outcomes, the power calculations can be made conservatively based on superiority hypotheses without specifying the equivalent margins. For continuous secondary outcomes, we would have over 80% power to detect outcome difference of 0.41 times the standard deviation based on paired t tests, with alpha=0.05, assuming equal outcome standard deviations for Insulclock and the conventional device, and within subject correlation equal to 0.3.

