# **STUDY SCHEDULE:**

FIRST PATIENT IN	2017 NOVEMBER
SCREENING	~200
RANDOMIZED	80
LAST PATIENT RECRUITED	2018
LAST PATIENT IN (COMPLETED)	2018 DECEMBER
DATA ANALYSIS	JUNE 2019- FEBRUARY 2019
SUBMISSION TO CONGRESS OR JOURNAL	ADA 2020 MAJOR MEDICINE JOURNAL AND/OR DIABETES CARE

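### The stated total of 150 patients contradicts the 80 on which the power section, the study schedule and the per-arm completer count rest

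*Combined protocol and SAP*

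**What the plan says.** Selection of Patients, under the number of subjects planned, states: "The total number of patients with T2D to be included in this pilot study is 150". The next sentence reads: "We anticipate a dropout rate of 10% - 20% through week 24 so that each arm will have 32 subjects at week 32".

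Power Considerations states: "This is a pilot study and we plan to recruit 40 subjects for each study group", and adds: "We assume no more than 15% attrition rate". It gives a 20-cell power table for the primary outcome, based on an exact binomial test at alpha 0.05. For continuous secondary outcomes it says "we would have over 80% power to detect outcome difference of 0.41 times the standard deviation based on paired t tests", with a within-subject correlation of 0.3.

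The Study Schedule has the row "RANDOMIZED 80", below a screening figure of about 200.

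On timing, Duration of study says: "The duration of this study will include a 26-week treatment phase and a safety clinic or telephone follow-up visit at week 28".

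**The concern.** The enrolment target appears in three places with two values. The section where a site, an ethics board or a later reader would look for it gives 150; the other two give 80. No text links them, and 150 is not the screening number, which the schedule puts at about 200.

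The plan has no interim analysis, so nothing formal governs stopping between 80 and 150. With both totals in the text, stopping at 80 can look like under-enrolment and going on to 150 like an unplanned extension, and neither could be shown to be prespecified. The power statement describes only one of the two trials.

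**Working it through.** **1. Totals side by side**

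| Section | Figure | Total |
|---|---|---|
| Selection of Patients | 150 in total | 150 |
| Power Considerations | 40 per group × 2 | 80 |
| Study Schedule | 80 randomized | 80 |

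Gap: 150 − 80 = 70, and 70/80 = 87.5%.

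**2. The 32 per arm.** Completers per arm = (N/2) × (1 − dropout), with 1:1 allocation (Methods).

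| N | 10% | 15% | 20% |
|---|---|---|---|
| 80 | 36 | 34 | 32 |
| 150 | 67.5 | 63.75 | 60 |

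From 75 per arm, ending with 32 would take 1 − 32/75 = 57% dropout. From 40 it takes exactly 20%.

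**3. The plan's primary power table.** Completers: n = 80 × 0.85 = 68. Discordant patients: m = n × Ptp, rounded, which gives 61, 54, 48, 41 and 34 for Ptp of 90% down to 50%. The test is an exact binomial test of p = 0.5 with at most 0.025 in each tail. The plan does not state sidedness, but one-sided versions do not reproduce the table. Power is the probability of falling in the rejection region under the assumed p. For m = 61 the region is 22 or fewer, or 39 or more; power is 31.2% at p = 0.6 and 87.9% at p = 0.7, as printed.

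All 20 cells reproduce: the 12 exact percentages to the printed decimal, and the 8 cells shown as above 99%. Among all completer counts from 40 to 150, only 68 matches all 12 exact percentages. From 120 to 135 none of the 12 matches.

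The p = 0.7 row:

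| Ptp | Printed | 68 completers (80 less 15%) | 120–135 completers (150 less 10–20%) |
|---|---|---|---|
| 90% | 87.9 | 87.9 | 98.6–99.5 |
| 80% | 83.7 | 83.7 | 97.2–98.9 |
| 70% | 74.9 | 74.9 | 94.9–98.0 |
| 60% | 66.5 | 66.5 | 92.1–95.7 |
| 50% | 55.4 | 55.4 | 83.8–92.3 |

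**4. The secondary power statement.** SD of the within-patient difference = SD × √(2 × (1 − 0.3)) = 1.183 SD. Paired t-test, two-sided 0.05, difference 0.41 SD, noncentral t:

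| Completers | Power at 0.41 SD |
|---|---|
| 64 (80 less 20%) | 77.9% |
| 68 (80 less 15%) | 80.4% |
| 120 (150 less 20%) | 96.4% |
| 135 (150 less 10%) | 97.9% |

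The plan's claim of just over 80% fits 68.

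**5. Smaller slips in the same sentence**

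(a) Dropout. The 32 per arm uses 20%, whereas the power section allows at most 15% (34 per arm). At 64 completers, 80% power for the secondary outcomes is reached at 0.421 SD instead of 0.408 SD. In the primary table the p = 0.7 row becomes 87.9, 83.6, 74.6, 65.9 and 49.5: four cells barely move, and the Ptp 50% cell falls by 55.4 − 49.5 = 5.9 points.

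(b) Timing. Week 32 lies four weeks after the week-28 follow-up that closes the study.

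**The case against.** The strongest reply concerns direction. A power section that fits 80 shows that it was calculated for 80, not that 80 is still the target. If the sponsor had later raised the target to 150 without updating the other sections, the text would look the same. This stands as a limit: the documents cannot prove which total is intended. It does not remove the contradiction, and the 32 per arm, in the sentence right after the 150, still fits 80 and not 150.

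A related point is that 32 per arm does not single out 80 by itself. At 10–20% dropout it corresponds to about 35.6 to 40 enrolled per arm, or roughly 71 to 80 in total. Likewise, 68 completers means 80 enrolled only with the power section's 15%. That is correct. The case for 80 rests on these figures together with the explicit 40 per group and 80 randomized, while 150 is ruled out as their source under any of the stated dropout rates.

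One could also argue that the harm is slight: the power calculation is correct for 80, enrolling 150 would only raise power, and no analysis is biased. All true. The reason to act is that the enrolment target is a basic design figure and has two values.

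**Conclusion.** The contradiction is real and 150 is the outlier. It exceeds by 70 patients (about 88%) the 80 used in Power Considerations and the Study Schedule, and it cannot yield 32 per arm at 10–20% dropout. The reproduction of the table assumes a two-sided exact test and a fixed, rounded number of discordant patients; under those assumptions all 20 cells are recovered at 68 completers. Confidence is high that the sections conflict and that the power section was built on 80. That 80 is also the intended target is the natural reading, which the sponsor should confirm. This must be fixed before the sample size is relied on. The dropout and week-32 slips are minor and do not drive that judgement.

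**What to change.** In Selection of Patients, change 150 to 80. If 150 is really intended, correct the 40 per group, the 80 randomized and the 32 per arm, and recompute the power section for 120–135 completers.

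In the same edit:

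- Use one dropout figure in both sections. With 15%, write 34 per arm, and the power section stands as printed. With 20%, keep 32 per arm, restate secondary power as about 78% at 0.41 SD (80% at about 0.42 SD), and recompute the primary table for 64 completers.
- Replace week 32 with the end-of-treatment week, once the 24-week statements (Study Aims, Assessment of Results) and the 26-week statements (Methods, Duration of study) have been reconciled.

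Cost: if 80 and 15% are confirmed, a change of wording only. With 80 and 20%, add a recomputed table and a slightly lower secondary power statement. If 150 is intended, the cost is 70 more patients than the power section and schedule provide for, plus a new power section.

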# Inclusion criteria:

Subjects meeting all the following criteria will be considered for enrollment into the study:

- 1. Age: 18 to 80 years
- 2. Diagnosis of T2D
- 3. Screening HbA1c  $\geq$  7.0% to  $\leq$  12.0%
- 4. Continuous treatment with one or more oral antidiabetic agents, for at least 2 months and/or

5. Continuous treatment with daily basal insulin (NPH, glargine U100 or detemir), for at least 2 months, (insulin dose  $\leq 0.5$  U/Kg/day).

6. If patients are on combination therapy of basal insulin and GLP1-RA, the dose of GLP-1 RA should be stable for the past three months.

7. Owns a smartphone compatible with the device

8. Signed, informed consent and HIPAA documentation

9. Subjects' ability to self-administer insulin, use the device and complete subject reported outcomes instruments

10. Subjects' ability & willingness to adhere to and be compliant with study protocol

# **Exclusion criteria**

1. Refusal or inability to give informed consent to participate in the study

2. Subject is currently taking or was treated with glargine U300 insulin, degludec, insulin dose greater than 0.5 U/kg/day during the previous three months

3. Subject treated with prandial insulin during the previous three months

4. Impaired renal function as shown by, but not limited to, eGFR < 30 ml/min.

5. Muscle weakness or hemiparesis related to previous stroke or myelopathy resulting in incoordination,

muscle weakness and inability to use pen device for insulin administration

6. History of diabetic ketoacidosis during the previous 6 months

7. Clinical evidence of active liver disease, or serum alanine aminotransferase (ALT) or aspartate

aminotransferase (AST) 3 times the upper limit of the normal range

8. History of hypoglycemia unawareness

9. Pregnancy or lactation

10. Known hypersensitivity to insulin glargine or any of the components

11. Any malignancy within the last 5 years, except for adequately treated basal or squamous cell carcinoma of the skin or adequately treated cervical carcinoma in situ

12. Current drug addiction or current alcohol abuse, or history of substance or alcohol abuse within the last 2 years

13. Diagnosis of dementia

14. Severe gastrointestinal diseases including gastroparesis

15. Cardiac status NYHA III-IV

16. Acute infection

17. Patients on or planning to receive long term oral or injectable steroid treatment for greater than 10 days

18. Patient schedule to undergo general surgery during the next 6 months

19. Any disease or condition that in the opinion of the investigator and/or sponsor may interfere with the completion of the study

# Potential Risks to the Subjects:

There are no major risks associated with the intervention.

**Hypoglycemia.** It is possible that following the proposed protocol, patients receiving basal glargine and metformin may develop hypoglycemia. For this analysis, **symptomatic hypoglycemia** is defined as an event with typical symptoms (i.e., sweating, palpitation, and feeling of hunger) with or without confirmation by plasma glucose <54 mg/dl (3.9 mmol/L).

Severe hypoglycemia is defined as episodes necessitating assistance and associated with measured plasma glucose < 40 mg/dl (2.2 mmol/L) or with prompt recovery after administration of carbohydrates, glucagon, or other resuscitative actions.

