### **Study Visits**

Screening (Visit 1)

Approximately 1-2 weeks prior to the start of the study, all potential study patients will be screened to check their eligibility after signing the informed consent form (ICF) and assigned a patient identification number. Medical history, physical examination, height, weight, vital signs, pre-existing conditions, and concomitant medications will be recorded during this visit. Laboratory assessments performed at Visit 1 to determine eligibility for the study include pregnancy tests for females, and HbA1c, serum chemistry, assays. Patients who do not meet all the inclusion criteria at Visit 1 will be considered screen failures and will not be randomized to participate in the study.

Eligible patients will be trained on the use of the glucometer to monitor their BG levels. Patients will be given diabetes diaries and associated training to record all glucose levels, insulin doses, and episodes of hypoglycemia.

Insulin administration technique will be reviewed prior to randomization to ensure good technique. Reinforcement will be provided as needed during the follow-up visits.

Only eligible patients treated with a once daily insulin dose of NPH, detemir, glargine insulin will be switched to SoloSTAR pen (glargine U100) at a total dose (TDD).

Antidiabetic agents will be continued at the same dose, except insulin secretagogues which can be stopped if HbA1c is <8% or reduced by half if HbA1c is >8%.

Patients will be instructed in performing glucose testing at home before meals, with a minimum of 2 out of the 4 pre-meal and bedtime glucose measurements per day. In addition, patients must perform a 7-point SMBG (fasting, before meals, 2 hours after meals, and bedtime) done between 3 to 5 days prior to Visit 2.

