One week after screening and before randomization, eligible participants will receive an Insulclock device. They will be properly trained on how to use it, charge and connect Insulclock to their mobile devices. Insulcloud will make smartphone available for subjects, who do not own a smartphone, during the course of the study. Technique skills such as the ability to navigate the app, press the button for 5 seconds while giving insulin injection, and how to connect the device to their phones will be explained. They will be asked to use the Insulclock with their insulin pen, to get familiarized with it. An assessment will be done after the week of using the device in order to review quality and understanding of the technology. Those subjects that fail to use the device properly will be deemed Screen Failures.

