# **Assessment of Results:**

The primary outcome of *treatment adherence* with the use of Insulclock with feedback or no feedback information (blinded) will be determined by the percentage of patients and number of insulin omission, mistiming and dosing. Number insulin irregularities will be registered on the Insulclock device and data will be retrieved during each clinic visit.

**For treatment satisfaction**, subjects' responses to questions 1, 7 and 8 of the DTSQc will be used. A comparison of the score on the DTSQs from week 12 to week 24 as well as using the score on the other questions of the DTSQc, which would overcome the ceiling limitation of using the DTSQs by itself, will also be used to assess treatment satisfaction . The Diabetes Treatment Satisfaction Questionnaire Status (DTSQs) form will be administered at weeks 0, 12 and 24.

Questionnaires will be given at week 0 for standardization purposes. The amplitude of the score on the DTSQc gives the degree of change in satisfaction while the direction (positive or negative) will provide guidance on the preference of one device over the other (i.e., if we predict that patients greatly prefer alarm reminders over nothing and he/she started the group 1 with daily reminders then transitioned to group 2 without the daily reminders, his/her score would be '-3', whereas if he/she was initially not getting the daily reminders followed by the daily reminders then the score would be '+3').

**Ouality of life** will be assessed at baseline and again at weeks 12 and 24 in order to determine the impact of the type of therapy on this outcome. Patients will be given the Diabetes Quality of Life Clinical Trial Questionnaire-Revised (DQLCTQ-R), the Problem Areas In Diabetes scale (PAID) and the Elderly Diabetes Burden Scale (EDBS) at baseline, weeks 12 and 24 to assess their quality of life and any potential impact of the treatment regimen .

*Glycemic Control* will be assessed via HbA1c at weeks -1, 12 and 24 and via fasting blood glucose averages at weeks 0, 12 and 24 from point of care testing during the preceding week.

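### The plan names no risk from missed-dose reminders and does not check the device log against the diary, so the log alone cannot reveal a repeat injection after an unlogged one

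*Combined protocol and SAP*

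**What the plan says.** Under Potential Risks to the Subjects, the protocol opens with "There are no major risks associated with the intervention". It then names one risk, saying that "patients receiving basal glargine and metformin may develop hypoglycemia". Neither that section nor Protection against Risks mentions the reminders.

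Under Methods, both groups carry the device. The feedback group gets daily information on its injections "as well as reminders in the event of missing doses". The other group "will use the Insulclock, but will not receive feedback on insulin treatment or alerts".

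The data source is given under Assessment of Results: "Number insulin irregularities will be registered on the Insulclock device and data will be retrieved during each clinic visit". Analysis of Primary Endpoint classes each patient's adherence as good or poor from three kinds of irregularity (omission, mistiming, dosing). No time window, dose tolerance or rule for an extra injection is given for any of them.

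A second record exists. Under Study Visits, patients receive diaries "to record all glucose levels, insulin doses, and episodes of hypoglycemia". Staff review the diaries at the randomization, interim, crossover and final visits. No section requires them to be compared with the device log.

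**The concern.** The reminders are the feature under test, so a hazard that they could create belongs in the risk statement and in the safety data. An electronic reminder about a missing dose presumably responds to the absence of a recorded dose. If a dose was given and not recorded, the reminder is false and the patient may inject a second time.

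Two things are at stake. The first is safety. The likely harm, hypoglycemia, is counted, but nothing links an event to a repeat injection. The titration text under Visit 14 asks whether a hypoglycemic event has an explanation, and Protection against Risks ties an insulin reduction to hypoglycemia. The two records that could supply the explanation are not brought together. No view is taken here on those clinical rules.

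The second is the primary endpoint. The same recording failure can be read differently in the two conditions, and the difference cannot run against feedback.

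**Working it through.** **1. The plan's own figures.** Power Considerations gives 40 per group and at most 15% attrition: 80 × 0.85 = 68 completers. With a two-sided exact binomial test against 0.5 at alpha 0.05, and 68 × P_tp rounded to 61, 54, 48, 41 and 34, the row for p = 0.7 comes out at 87.9, 83.7, 74.9, 66.5 and 55.4%, as printed. The p = 0.6 row and the two numeric cells at p = 0.8 also match. So 68 is the number the plan itself works with. (The section on planned numbers says 150, while Study Schedule says 80; the table fits 80.) Nothing below alters this table.

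**2. One day on which an injection is given but not logged.**

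| Condition | What follows | Injections given | Log entries | How the log reads |
|---|---|---|---|---|
| Feedback, patient does not act on the reminder | nothing | 1 | 0 | omission |
| Feedback, patient injects again and this is logged | duplicate | 2 | 1 | adherent or mistimed (no window defined) |
| No feedback | no reminder | 1 | 0 | omission |

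The duplicate in the second row leaves a single entry. Only a diary in which the first injection was written down could reveal it.

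**3. Effect on apparent omissions per patient.** Let u be the share of given injections that go unlogged and q the share of false reminders followed by a second, logged injection. Assume one dose a day, always given, for 12 weeks × 7 = 84 days.

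- Without feedback: 84u apparent omissions.
- With feedback: 84u(1 − q).
- Difference: 84uq, which is also the expected number of duplicates.

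At u = 5% and q = 20% this is 4.2 against 3.36, a difference of 0.84 per patient. The chance of at least one duplicate is 1 − (1 − 0.05 × 0.20)^84 = 57%. At u = 1%, q = 5% the difference is 0.04 and the chance 4%. At u = 10%, q = 50% they are 4.2 and 99%.

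**4. Trial total.** Scheduled doses under feedback: 68 × 84 = 5,712.

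| u | q | 5,712 × u × q |
|---|---|---|
| 0.5% | 5% | 1.4 |
| 2% | 20% | 22.8 |
| 1% | 5% | 2.9 |
| 5% | 20% | 57.1 |
| 10% | 50% | 285.6 |

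Every value of u and q is an assumption; the documents give neither. The plan also states a 26-week duration in places. A 13-week period would multiply expected counts by 91/84 = 1.08.

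**The case against.** The strongest reply is that the causal chain is not in the documents. Study Visits lists training topics and does not say what creates a record. A reader might take "press the button for 5 seconds while giving insulin injection" as a logging step, but it is described as part of giving the injection and carries a citation to an insulin-administration reference, so it may be ordinary injection technique. How a reminder is triggered is not described in detail. This stands: that an injection can go unlogged is an inference, made plausible by the need to charge the device and connect it to a phone.

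A reader might also infer that the hazard is invisible in the planned data. It is not. The diary records doses and is reviewed at visits, hypoglycemic events are compared between groups, and contact is every two weeks. What is missing is the written step that joins diary and log. The one-week trial of the device before randomization, with screen failure for improper use, lowers the risk but does not test for recording failures in later months.

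A third tempting reading is that the log would score a duplicate as good adherence. That is not established. A second injection after a reminder may be late enough to count as mistimed, and two logged injections might fall in the undefined dosing class.

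Finally, feedback could also prevent duplicates, because patients see the time and amount of their injections, whereas a patient without feedback might forget an injection and repeat it. The net difference in duplicates is therefore unknown. That is a reason to count them in both conditions.

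**Conclusion.** The point holds as a gap in the risk statement and in data handling. The plan does not address repeat injection after a false reminder, has no count of scheduled doses with two injections, and does not require reconciliation of log and diary. If injections sometimes go unlogged and some patients act on the resulting reminder, the log hides the duplicate. It also shows fewer omissions under feedback than the same failure produces without it. On the good-or-poor endpoint the effect is in favour of feedback, or nil where the late injection is scored as an irregularity anyway.

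The size cannot be set from the documents. The illustrative range, about 1 to 286 duplicates, runs from negligible to common, so the case rests on mechanism and direction alone. The documents do not support saying that duplicates will occur often, or that the adherence result would be explained by them.

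**What to change.** 1. **Potential Risks to the Subjects:** name repeat injection after a false missed-dose reminder as a possible risk of the intervention.
2. **Assessment of Results:** compare diary and device log on days with a reminder under feedback, and on days of apparent omission without feedback, so that both conditions are checked.
3. **Statistical Analysis and the endpoint sections:** report by condition the number of scheduled doses with two injections, from diary and log together, alongside hypoglycemic events. Classify such days as dosing irregularities, at least in a sensitivity analysis of the primary endpoint.

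The cost is protocol and SAP wording plus some data-management time, since both records are already collected. The documents do not say whether reminder times can be exported. If they cannot, reminder days would have to be derived from the log once a missed dose is defined. One limit remains: the diary detects a duplicate only if the patient wrote down the first injection. No dose or clinical rule is proposed.
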